#### Biplane Fluoroscopy Laboratory / Radiological Imaging Session – If needed

If for any reason we are unable to capture all of the fluoroscope or radiologic images we need during the prior visit(s), or if we found any problems with the images afterwards, we will ask participants to come in for an additional session to repeat or complete procedures as needed.

#### Registry

Participants will be asked if they are interested in joining our Center's Subject Registry (MIRB# 00433). This registry is used to recruit for studies being conducted by our Center. If participants choose to join the registry they will sign a separate consent form. Data about their foot/alignment type that is collected under this study will be added to the Subject Registry; this will help us determine which studies may be a good fit for participants in the future.

#### Repository

Participants will be asked if they are interested in allowing their study data to be added to our de-identified data repository so that it may be used for additional research in the future. Participants who are interested will be asked to sign a separate consent form for the repository (MIRB# 00493).

#### Additional use of de-identified data

Throughout the course of the study we will place a copy of all de-identified data in publicly accessible online data repositories. Once posted, the de-identified data will be publicly accessible to search, retrieve, and analyze for any purpose. Participants will be made aware of this use of de-identified data during the consent process and it will be described in the consent form. If participants do not

wish to have a copy of their de-identified data placed in online repositories they can choose not to participate in the study.

### **Payment to Participants**

Participants will be paid \$25/hr for each study visit. Participants that attend the first visit but are screened out will be compensated for that visit. Payments may be issued in cash or check (participant preference). Checks will be mailed about 6-8 weeks after each visit, or cash payments can be collected through the agent cashier at the VA Puget Sound approximately 6-8 weeks after each visit.

### **Risks and Risk Management**

#### **Procedures Involving Radiation Exposure**

There is a very small increased risk of cancer due to the amount of radiation exposure involved in this study. Based on previous Radiation Safety Applications by our research group, and using conservative estimates, the estimated radiation exposure is from two sources (a) the CT scans of subject anatomy, and (b) the fluoroscope imaging and (c) x-rays of static limbs, including long leg x-ray. For risk (a), the CT imaging is conservatively estimated to expose participants to 0.2 mSv of ionizing radiation and for the fluoroscopic exposure (b) an estimate (again conservative) of 0.20 mSv for 80 gait trials and (c) an estimate of 0.07 mSv. The total estimate of exposure is 0.47 mSv. For comparison, this total dose is less than a quarter of the exposure for a single head CT scan. Further, the upper limit of radiation exposure involved in this study is approximately 1/7th of the estimated naturally occurring background radiation exposure (of 3.1 mSv) (<http://hps.org/documents/>) "Background Radiation Fact Sheet." For additional comparison, the EPA (<https://www.epa.gov/radiation/radiation-sources-and-doses>) estimates of annual radiation exposure is 6.20 mSv (3.1 mSv from naturally occurring background radiation and 3.1 mSv man-made sources such as equipment used in medical procedures), this study will therefore expose participants to ~7.5% of the annual background radiation. Please note that this is the maximum anticipated exposure, in practice we find that participants normally complete their walking trials in well under 80 attempts, but we wish to be conservative with our estimate. We will minimize the risk due to radiation by taking the minimum number of fluoroscope trials needed to obtain the necessary data. This means that some participants may only require 30 trails (potentially less), which will reduce the total radiation exposure. It is anticipated that most participants, particularly controls, will be well under the 80 exposures we have budgeted for in our radiation estimate. Existing x-rays and CT scans will be used whenever possible.

It is possible that participants may be exposed to loud noises (like a heavy door slamming) when they are inside the building that houses the biplane fluoroscopy lab; this may startle some individuals. The building where lab is located also houses a blast machine. The blast machine is located in a separate lab, diagonally across the building from the biplane fluoroscopy lab. The blast machine can be quite loud when standing directly outside of the door of the lab where it is located, however when walking to or when inside the fluoroscopy lab the noise sounds like a muted bang/door slamming. We have a

set of standard operating procedures that will be followed in order to minimize the risk that participants will be exposed to noises from the blast machine. The SOPs include escorting participants at all times and informing them of the potential noises prior to entering the building.

It is possible that participants could trip and fall during the walking procedures. The the biplane imaging walkway is clear of obstacles and is level, dry, and rigid. Thus, walking on the biplane walkway is akin to walking on a well-maintained sidewalk. The biplane walkway also has support railings on both sides; these railings will be within easy reach of participants at all times. Participants will also have time to familiarize themselves with the shoes and the area in which they will be asked to walk.

Participants may feel a mild level of emotional stress if they find it inconvenient to travel to the VA for study visits, or if they have difficulty sitting or standing still during the x-rays or CT scan. Participants will be instructed to let us know if they would like to take break during procedures, and they can opt out of the study at any time.

#### Inflicted Insight

It is possible that we could discover that female participants are pregnant. It is also possible that the imaging procedures (CT scans, X-rays and fluoroscopic images) could reveal that a participant has a serious health problem or anatomical abnormality (e.g., bone cancer). Potential participants will be screened during the telephone call, or in person screening, regarding their willingness to be made aware of the pregnancy test result and/or potential health problems discovered by the imaging procedures. Those who are not willing to be told about this information will be excluded from the study. Additionally, in the consent form, participants will again be made aware of this possibility and given the option to decline participation in the study if they choose. If a participant is determined to be pregnant and/or if we see an unexpected abnormality in a participant's radiological images we will advise them to follow up with their regular health care provider.

#### Wedge insole comfort

It is possible, although unlikely due to the brief nature of the data collection trials, that participants may experience discomfort or pain while standing and walking with the wedged insoles or study shoes. If this occurs it would likely be discovered immediately at the start of testing for a given wedge condition. Participants may experience mild soreness or soft tissue irritation (e.g., a blister) from walking with shoe inserts and/or in shoes that are unfamiliar, either during or shortly after the study sessions. Participants with ankle OA may experience a small increase in ankle or foot pain during or shortly after the study sessions. Participants will be instructed to inform us if they feel discomfort or pain and the procedures will be stopped so that we can adjust/re-fit the shoe/insole. If we are unable to achieve a comfortable fit the study session will be ended. Care will be taken to properly fit the shoes. Participants can take breaks at any time.

## Quality Control

The PI will ensure the study procedures are being properly followed by keeping the research staff well informed of the current study procedures through regular/ongoing contact and meetings. The PI and/or designated research staff will verify visually that the data are sufficient and accurate as soon as possible after each data collection visit is complete.

## Privacy and Confidentiality

See section 7.0 below for Information Security, Privacy and Confidentiality related procedures.

## **5.6 Data Analysis**

### **Plan and Hypotheses:**

Hypothesis 1: During gait, there are different tibio-talar kinematics between OA participants with static varus alignment, OA participants with static valgus alignment, and controls.

Linear mixed effects regression will be used to test for differences in gait kinematic measures coronal plane alignment being the primary dependent variables by OA group (clinical OA varus, clinical OA valgus or controls, the independent fixed effects). Study subject will be modeled as a random effect. If the omnibus test for association between gait kinematic measure and OA group is significant, then pair-wise comparisons will be carried out.

Hypothesis 2: Some static neutrally aligned OA participants will exhibit varus or valgus tibio-talar misalignment when measured dynamically using biplane fluoroscopy.

To determine the potential miss-categorization of OA neutrally aligned participants: frequencies, percentages and 95% confidence will be estimated for the number of participants in the OA static (from standing radiograph) neutral group who are classified into varus, valgus or neutral using dynamic measures (from fluoroscopy trials).

Hypothesis 3: OA participants with static (varus/valgus) tibio-talar misalignment will exhibit reduced misalignment when walking with (lateral/medial) wedge insoles.

Linear mixed effects regression will be used to test for improvement in misalignment, i.e. the reduction in coronal plane disparity between OA and control participants (the dependent variable) when walking with a wedge vs. no wedge (the independent fixed effect) for OA varus and OA valgus participants separately. Subject and subject-x-wedge interaction (the latter to account for variability across multiple trials in the difference in within subject misalignment by wedge use) will be modeled as random.

Hypothesis 4: OA participants with static neutral alignment, but with dynamic (varus/valgus) tibio-talar misalignment will exhibit reduced misalignment when walking with (lateral/medial) wedge insoles.

This will be tested using the same methods as Hypothesis 3, substituting OA varus and valgus participants (from static radiographs) to those who are neutral in static radiography, yet varus or valgus dynamically.

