### Biplane Fluoroscopy – Baseline

While wearing shorts (their own or ones we provide), participants will change into standard lab shoes and enter the Biplane Fluoroscopy Laboratory. Participants will step onto an elevated walkway, which is flat, about 3-feet wide, level, and has handrails on both sides. They will be asked to walk freely up and down the walkway to get comfortable with the test environment. External markers may be placed on the shoe for tracking purposes. While participants stand still on the platform, two fluoroscopes will capture simultaneous X-ray images of the participants' foot of interest, to record the standing position of the foot bones. These dual fluoroscopes allow for tracking of the bone motion in three dimensions (3D) while participants walk. Next, participants will be asked to walk along the platform while simultaneous X-ray images of the foot of interest are taken; each X-ray exposure is expected to last about 0.5 seconds, and will image from about 3 inches above the ankle to below the bottom of the shoe or foot. This set of standing and walking trials may also be

conducted with a neutral insert in the shoes, or barefoot. With some participants, we may capture images of each foot during the standing and walking X-ray procedures.

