#### Biplane Fluoroscopy – Wedged Insoles

Research staff will insert one of the wedged insole configurations (selected based on the participants' varus/valgus indication) into both of the participants' shoes. Participants in the control group may be asked to do these procedures with several different insole configurations. Participants will then repeat the standing trial, and then perform walking trials in the same format described above. With some participants, we may capture images of each foot during the standing and walking X-ray procedures. Participants will be instructed to let us know if they feel pain or discomfort during the procedures. If the shoes or inserts feel uncomfortable, we will attempt to re-fit them, if we are unable to achieve a comfortable fit, we will stop the procedures.

We will not ask participants to walk through our active fluoroscopic imaging system more than 80 times total during the entire study, and as noted above the total radiation exposure for the study will not exceed 0.47 mSv.

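### Hypothesis 4 selects ankles on dynamic alignment and does not keep the classifying no-wedge trials out of the wedge versus no-wedge comparison; if they are reused, regression to the mean favours the hypothesis

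*Combined protocol and SAP*

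**What the plan says.** Under Hypothesis 2 (section 5.6, Plan and Hypotheses), static-neutral OA participants are those "who are classified into varus, valgus or neutral using dynamic measures (from fluoroscopy trials"). The text does not say which trials classify an ankle, how they are summarised, or what the cut is.

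Hypothesis 3 compares alignment "when walking with a wedge vs. no wedge (the independent fixed effect) for OA varus and OA valgus participants separately", with subject and subject-by-wedge random effects. Its groups come from static radiographs. Hypothesis 4 takes over that method, "substituting OA varus and valgus participants (from static radiographs) to those who are neutral in static radiography, yet varus or valgus dynamically".

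Section 5.5 describes the data. At baseline, "participants will be asked to walk along the platform while simultaneous X-ray images of the foot of interest are taken". The baseline set may also be "conducted with a neutral insert in the shoes, or barefoot", but this is optional and has no assigned role in the analysis. The wedge trials follow in the same format. A further visit is foreseen only if images are missing or faulty, when participants "come in for an additional session to repeat or complete procedures as needed".

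**The concern.** Hypothesis 4 uses dynamic alignment twice: once to choose the ankles and once as the outcome. If the same no-wedge trials do both jobs, ankles whose trial error happened to point outward are over-represented, and that error sits in the no-wedge arm. The wedge trials carry fresh error, so they lie closer to neutral on average even when the wedge does nothing. The bias points toward the study hypothesis.

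Hypothesis 3 does not have this problem, because its ankles are chosen on a different measurement. Its method therefore does not transfer unchanged, and its random effects do not correct for selection on the outcome. At stake is how to read a small positive Hypothesis 4 result, of a few tenths of a degree, in what may be a small subgroup.

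**Working it through.** **The plan's own figure.** The only power statement is for Hypothesis 1. With 30 and 20 participants, SDs 1.8 and 2.9, 3 trials and trial error 1.5, the variance of the difference is (3.24 + 0.75)/30 + (8.41 + 0.75)/20 = 0.591, so the standard error is 0.769. Then 3.5/0.769 − 1.96 = 2.59, a power of 99.5%. The stated figure of more than 99% reproduces. It says nothing about Hypothesis 4.

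**Inputs from the plan.** Trial error σ = 1.5 degrees; up to 40 static-neutral OA ankles; between-ankle SD s = 1.8 (pilot OA) or 2.9 (pilot controls), neither measured in static-neutral ankles. Three trials is the count in the Hypothesis 1 power section; none is given for Hypothesis 4.

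**Assumptions.** True wedge effect zero; ankles centred on the reference; cut c = 2 degrees; classification on the mean of the same k no-wedge trials that form the no-wedge arm.

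**Formula.** Let T = √(s² + σ²/k) and λ(z) = φ(z)/(1 − Φ(z)). The expected spurious reduction is (σ²/k)/T × λ(c/T), and the expected number selected per direction is 40 × (1 − Φ(c/T)).

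For s = 1.8 and k = 3: σ²/k = 0.75, T = √3.99 = 1.997, c/T = 1.001, λ = 1.526. The bias is 0.3755 × 1.526 = 0.573 degrees, with 40 × 0.1583 = 6.3 ankles.

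| No-wedge trials | Bias, s = 1.8 | False benefit | Bias, s = 2.9 | False benefit |
|---|---|---|---|---|
| 3 | 0.57 | about 18% | 0.31 | about 11% |
| 6 | 0.31 | 11–12% | 0.16 | about 8% |
| 10 | 0.19 | about 8% | 0.10 | about 6% |

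The false-benefit rates are simulated, per direction, by paired test on ankle means, against 2.5% nominal. About 6 (s = 1.8) to 10 (s = 2.9) ankles are selected per direction.

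**Planned mixed model.** The plan names no degrees-of-freedom method. At 10 trials and s = 1.8 the rate under reuse is 2.2% with t on n−1 df and 8.2% with Wald z. At s = 2.9 it is 3.0% and 5.3%. The near-nominal figures with t reflect a conservative test: with trials split 5/5 at s = 1.8, the same two methods give 0.2% and 1.9%. The 0.19-degree bias in the estimate remains.

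**Sensitivity at 3 trials.**
- A cut of 1 degree gives 0.25 to 0.43 degrees; a cut of 3 degrees gives 0.38 to 0.73.
- If the group centre lies 3.5 degrees off the reference, the cut sits at 2 − 3.5 = −1.5 from the centre. The bias is 0.13 to 0.15 degrees (about 0.04 at 10 trials), with about 28 to 31 ankles and a false-benefit rate of about 8 to 10%.
- If classifier and outcome share trial error with correlation 0.5, the bias is 0.29 degrees and the rate 7% (s = 1.8); at 0.25, 0.15 degrees and 4.5%.

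**Separating the trials.** Cross-fitting two halves leaves at most 0.02 degrees of bias toward the hypothesis; a pooled version with only 3 trials gave about −0.03, slightly against it. False benefit is 1.8 to 2.5%.

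**The case against.** The best case for the plan has four parts.

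First, reuse is not stated. The optional neutral-insert set could serve as comparator, and several visits are allowed. This stands: a reader might infer that Hypothesis 4 is biased as written, and the documents do not go that far. They do leave one required no-wedge set and no rule for dividing it.

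Second, the larger figures rest on unfavourable choices. This also stands. The pilot means (−1.8 and 1.7) differ by 3.5 degrees, and an offset of that size cuts the bias to 0.13–0.15 degrees at 3 trials. The risk section mentions some participants needing only 30 trials in all, so more than 3 per condition is plausible. The additional analyses use peak talar surface angle and talar tilt, so classifier and outcome may share only part of their error. Size depends on these choices; direction does not, provided some trial error is shared.

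Third, reserving trials could damage Hypothesis 2. It would if Hypothesis 2 were restricted too. At s = 1.8, one trial out of three classifies 7.9 ankles per direction, against 5.3 truly beyond the cut, and only 47% of those chosen are true; all three trials classify 6.3, with 66% true. Hypothesis 2 needs no separation and should keep every trial.

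Fourth, separation does not remove stable subject-by-wedge variation, which the plan models. With an assumed variance of 0.5 per condition (s = 1.8), 0.37 degrees remains after a 5/5 split and 0.38 with a repeat block of 10. Part of that is a real difference between conditions, but the limit should be stated.

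**Conclusion.** The gap is real and the direction is clear: if the classifying trials also form the no-wedge arm, Hypothesis 4 leans toward its own conclusion. Under the centred, 2-degree, fully shared-error assumptions the spurious reduction runs from 0.57 degrees (3 trials, SD 1.8) to 0.10 (10 trials, SD 2.9). It is about 0.04 at 10 trials with a 3.5-degree offset. The count of 6 to 10 ankles per direction holds only under the centred assumptions.

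Two stronger inferences are not supported. A positive Hypothesis 4 result would not be an artefact as such: a change of several degrees is far outside these figures, and only a few tenths of a degree is open to doubt. Nor does the point reach Hypothesis 3, whose groups are set by static radiographs. This is a cheap improvement to the plan.

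**What to change.** Change the Hypothesis 4 analysis only.

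- Keep the Hypothesis 2 classification on all no-wedge walking trials, and name the classifying measure and cut.
- For Hypothesis 4, divide each ankle's no-wedge walking trials into two pre-designated halves, for example alternate trials. Classify on one half and take the no-wedge value from the other; then swap, and combine the two with a standard error clustered on ankle.
- Report any contrast that reuses the classifying trials as descriptive only.
- Name the degrees-of-freedom method for the mixed model.
- State that this removes trial-error bias only. Stable subject-by-wedge or session-level variation would remain. The plan gives no figure for either, so whether a separate no-wedge block is worth having cannot be settled here.

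The change is to analysis text and leaves the choice of insole configuration in section 5.5 alone. Precision is nearly unchanged: at 10 trials and SD 1.8, the SD of the estimate is 0.29 degrees against 0.28 under reuse. The price is slightly more analysis work and noisier selection of ankles for Hypothesis 4, mainly at 3 trials, where one half is a single trial.

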### **Additional Analyses:**

1) Ankle misalignment likely varies during gait, and the pose of the foot during peak misalignment may not correlate with the position of the foot in the clinical 2D X-ray. To investigate this, the peak misalignment (varus or valgus) during gait as measured from the talar surface angles and talar tilt in data set 2 will be compared to the peak from the static standing fluoroscopic, this will be done for all groups. The result will be a measure of how frequently current clinical measure captures true maximum misalignment during gait.

2) The methods used to generate data set 2 can be used to re-create any 2D position from the 3D kinematics. Considering additional analysis 1, we may identify a phase of gait that more reliably demonstrates maximum misalignment (e.g. at heel rise). At the peak misalignment during that phase, we will generate additional simulated 2D X-ray images, in perspectives which would be possible to capture diagnostically (e.g. straight AP views and minor variations). In these new views, we will re-measure the talar surface angle and talar tilt. Such an exploration requires no additional subject X-ray exposure, as it is a digital processing of the data already collected. The result may be a 2D X-ray imaging angle / foot pose combination which is better suited than current methods for detecting maximum misalignment. This information may have immediate clinical benefit and will be rigorously pursued with additional study.

3) In a similar vein, we will perform a sensitivity test on the current clinical imaging methods. We will generate a series of 2D X-ray image planes by varying the standard clinical AP X-ray perspective in 1 degree increments about the SI and ML axes. Talar surface angle and talar tilt will be recalculated for each of these perspectives. By replicating this measure over a range of  $\pm 15$  degrees, we will determine the sensitivity of the clinical measure to foot positioning during diagnostic imaging.

The preceding three additional analysis serve to determine: (1) the ability of current methods to determine peak misalignment, (2) if a clinical angle / pose exists that is more diagnostically meaningful, and (3) the sensitivity of positioning to the current clinical method.

4) Transverse alignment of the ankle joint is technically more challenging to diagnose due to the need of such an superior / inferior image to pass through the tibia. With the methods described above, we can perform these measurements without difficulty. Using a similar regression and criteria as in Hypothesis 1, we will evaluate differences in transverse plane alignment during gait. Additional measures will compare the changes in malleolar / talar dome side spacing and the closest approach of the transverse borders of the malleoli to the talus. This may identify abnormal transverse wear patterns within the ankle joint – a measure that will not only benefit prevention, but that has significance in ankle replacement.

5) We will use a similar regression as in Hypothesis 1 to determine if there are differences in gait kinematic measures between OA varus / valgus (from static radiograph) and OA varus / valgus (from fluoroscopy trials). This will indicate whether these groups exhibit similar kinematics during gait, despite different static diagnostic determination.

6) We may find participants who do not benefit from wedge insoles (non-responders), depending on both the presence and size of these subgroups; this will yield pilot data to support identifying and investigating these subgroups in follow up proposals.

